15. EFFICACY OUTCOMES

15.1. PRIMARY EFFICACY

15.1.1. PRIMARY EFFICACY VARIABLE & DERIVATION

The primary efficacy endpoint is:

- The proportion of patients in each treatment group with a clinical response (CDAI decrease of ≥ 70 compared with baseline) at Week 4

CDAI decrease at Week 4 is assessed as the decrease relative to baseline measurement:

- Decrease = CDAI at Baseline - CDAI at Week 4

In case of baseline value equal to 0 or missing post-baseline value recorded, then the change is set to 0 for the corresponding visit (no decrease).

Subjects with a decrease greater or equal to 70 are responders. Other subjects are considered as non-responders.

15.1.2. MISSING DATA METHODS FOR PRIMARY EFFICACY VARIABLE

No missing data for the primary analysis endpoint are expected for the FAS, because Week 4 is the first post-baseline visit for efficacy assessment and, in case of discontinuation prior to Week 4, the EoT efficacy assessments should be performed.

The non-responder imputation principle will be followed for the FAS. CDAI evaluation will be set to non-

Document: \\ieedc-vnasc01\BIOSdata\Boehringer_Ingelheim\BI_695501\NVA96252\Biostatistics\Documentation\SAP\BI1297.4 SAP FINAL v4.0_22MAY2019.docx

Author: Version Number: Final V4.0
Version Date: 22MAY2019

Template No: CS_TP_BS016 Revision 5
Effective Date: 01Apr2018

Reference: CS_WI_BS005

responder at Week 4 if the subject:

- discontinues treatment prior to Week 4
- is lost-to-follow-up (according to eCRF record for “End of Treatment” or “Trial Completion”) prior to Week 4

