7.3.1 Primary endpoint analyses

Primary efficacy analysis:

The primary analyses will be performed on the FAS. Patients will be assigned to the treatment they were randomized to receive.

The primary analysis of the observed proportion of patients with a clinical response (CDAI decrease of \geq 70 compared with baseline) at Week 4 will be based on log-linked binomial model. No missing data imputation for primary analysis endpoint need to be taken into account due to FAS definition. However, for pre-specified criteria non-responder imputation (NRI) will be applied (see Section 7.5).

The statistical model can be described as follows:

• (M1) Response to treatment at Week 4 = treatment + prior infliximab exposure + screening SES-CD

This model includes the stratification factor, prior exposure to infliximab, and treatment as fixed, categorical effects and it will be investigated whether the baseline SES-CD will be included as a continuous or as a categorical effect:

- Treatment (BI 695501, EU-approved Humira)
- Prior exposure to infliximab (Yes/No)
- Baseline SES-CD ($<16 \text{ or } \ge 16$)

The relative risk estimate together with its 90% and 95% CI (ratio scale) will be produced.

Further efficacy analyses:

As sensitivity analyses to the primary analysis, the primary endpoint will also be analyzed on the PPS with NRI.

The following explorative hypotheses are not intended to support any biosimilarity claim for BI 695501; however, the framework of non-inferiority testing will be used to compare efficacy of BI 695501 versus EU-approved Humira in a descriptive way.

The following hypotheses will be investigated:

- H_0 : RR of proportion of patients with a clinical response (CDAI decrease of \geq 70 compared with baseline) at Week 4 (BI 695501 versus EU-approved Humira) is less than or equal to 0.76
- H₁: RR of proportion of patients with a clinical response (CDAI decrease of ≥70 compared with baseline) at Week 4 (BI 695501 versus EU-approved Humira) is greater than 0.76

Two-sided 90% CI will be used for the comparison.

The applied margin (0.76 on the ratio scale for CDAI 70) does preserve 39% of the historical effect of adalimumab over placebo (based on a meta-analysis of GAIN and CLASSIC1; see Appendix 10.3 for further details).

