7.5 HANDLING OF MISSING DATA

7.5.1 Efficacy endpoints

No missing data for the primary analysis endpoint are expected for the FAS, because Week 4 is the first post-baseline visit for efficacy assessment and, in case of discontinuation prior to Week 4, the EoT efficacy assessments should be performed. However, all patients who

discontinue treatment, are lost-to-follow-up or have any major protocol deviation related to any therapy that may significantly impact efficacy assessment (Table 4.2.2.1: 1) prior to the primary endpoint assessment will be considered as non-responders. Patients without any available CDAI evaluation at Week 4 will also be considered as non-responders. This is referred to as 'NRI'. Patients assessed as non-responders at Week 4 will be considered non-responders for all subsequent time points (LOCF).

For secondary efficacy endpoints, rules for handling of missing data will be specified in the TSAP, if necessary.

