3.3. CHANGES TO ANALYSIS FROM PROTOCOL

No change to analysis from protocol is planned.

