15.2.2. MISSING DATA METHODS FOR SECONDARY EFFICACY VARIABLE

Missing CDAI at Week 24 will be imputed using the combination of NRI and LOCF methods. Only the data up to Week 24, inclusive, will be considered.

The following table details exactly where the NRI / LOCF imputation method will be applied for the sensitivity analysis.

Table 1: Application of LOCF / NRI for the secondary analysis on the FAS

Secondary analysis (FAS)	prior to/on Week 24	
	Discontinued treatment [#]	Did NOT discontinue treatment
CDAI computable using observed data at Week 24	Observed	Observed
CDAI NOT computable using observed data at Week 24	NRI applied	LOCF applied

[#] lost to follow-up (according to eCRF record for “End of Treatment” or “Trial Completion”) is also included here, or patients who took a therapy that may significantly impact efficacy assessment prior to this time-point.

The following steps will be followed:

STEP 1:

Missing CDAI score will be imputed using LOCF method and CDAI will be calculated based on the imputed scores. Last observation will be carried forward as many times as needed.

STEP 2:

NRI principle will be considered at Week 24 as detailed in section 15.1.2.

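### SAP 15.1.2 drops, without declaring it, the protocol 7.5.1 rule that a major deviation involving an efficacy-relevant therapy before the Week 4 assessment counts as non-response

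*SAP*

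**What the plan says.** Protocol 7.3.1 says of the primary analysis that "for pre-specified criteria non-responder imputation (NRI) will be applied", and points to protocol 7.5 for the criteria. Protocol 7.5.1 makes a patient a Week 4 non-responder on any of three grounds arising before the primary assessment. These are stopping treatment, being lost to follow-up, or being among those who "have any major protocol deviation related to any therapy that may significantly impact efficacy assessment", with a reference to Table 4.2.2.1: 1. It adds patients with no Week 4 CDAI.

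SAP 15.1.2 states "The non-responder imputation principle will be followed for the FAS", followed by two bullets: treatment stopped before Week 4, and loss to follow-up before Week 4. SAP 15.1.1 defines the endpoint: "Subjects with a decrease greater or equal to 70 are responders". SAP 3.3 says "No change to analysis from protocol is planned", and SAP 1 names Protocol Version 3.0 as its basis, which is the version containing the three-part rule.

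The SAP does name the therapy trigger once, for Week 24. The footnote to Table 1 in SAP 15.2.2 adds "patients who took a therapy that may significantly impact efficacy assessment prior to this time-point" to the discontinued column.

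**The concern.** The responder definition for the primary endpoint depends on which document is followed. A programmer working from SAP 15.1.1 and 15.1.2 would count a patient whose CDAI fell by 70 or more after, say, a prohibited escalation of Crohn's medication as a responder to trial drug. The protocol counts that patient as a non-response because the fall cannot be credited to the assigned treatment.

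At stake are the Week 4 response rates, the relative risk and its 90% and 95% intervals. SAP 4.2 repeats the primary analyses at the final analysis, so the gap would appear there too.

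**Working it through.** **1. The rules side by side**

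| Situation before the Week 4 assessment | Protocol 7.5.1 | SAP, Week 4 |
|---|---|---|
| Treatment stopped | non-responder | non-responder (15.1.2) |
| Lost to follow-up | non-responder | non-responder (15.1.2) |
| No Week 4 CDAI | non-responder | non-responder (15.1.1 sets the change to 0) |
| Major therapy deviation, still treated, observed fall below 70 | non-responder | non-responder (15.1.1) |
| Major therapy deviation, still treated, observed fall of 70 or more | non-responder | **responder** (15.1.1) |

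Only the last row differs.

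**2. Can the last row occur?** Partly it is pre-empted. Protocol 3.3.4.1 takes a patient who needs an interfering drug off treatment, and protocol 4.2.2.1 does the same for surgery; both then fall under the first SAP bullet. But Table 4.2.2.1: 1 also bars escalation of Crohn's treatments and requires a steady corticosteroid dose until Week 4. A breach of these is not in itself a listed reason for stopping in 3.3.4.1, and protocol 4.3 says only that a patient who violates restrictions may be discontinued. Protocol 7.5.1 lists discontinuation and therapy deviation separately, so it treats them as distinct.

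**3. Is it caught elsewhere?** Not reliably. The items named in SAP 5.4 for the per-protocol set are wrong medication, dosing compliance and entry criteria. The list is open-ended, so removal is possible but not required. SAP 9.1 lists prohibited concomitant treatment as an important violation, but says the violations tabulated from the deviations log are not the ones that exclude patients from either per-protocol set.

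**4. Size (illustration only).** Inputs from protocol 7.7: 65 per arm and 80% response, so 0.80 × 65 = 52 responders per arm. The plan's own precision reproduces as a risk-difference half-width: 1.645 × √(2 × 0.8 × 0.2 / 65) = 0.1154, stated as 0.115.

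For the primary measure, unadjusted: RR = x₁/x₀, SE(log RR) = √(1/x₁ − 1/65 + 1/x₀ − 1/65), 90% CI = RR × exp(±1.645 × SE). The number of affected patients and their arm are assumptions.

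| Responders reclassified | x₁ / x₀ (BI 695501 / Humira) | RR | 90% CI |
|---|---|---|---|
| none | 52 / 52 | 1.000 | 0.866–1.155 |
| 1 in BI 695501 | 51 / 52 | 0.981 | 0.846–1.137 |
| 2 in BI 695501 | 50 / 52 | 0.962 | 0.827–1.119 |
| 3 in BI 695501 | 49 / 52 | 0.942 | 0.807–1.100 |
| 3 in Humira | 52 / 49 | 1.061 | 0.909–1.239 |
| 3 in each arm | 49 / 49 | 1.000 | 0.848–1.179 |

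One patient in one arm moves the RR by about 0.02 (52/51 = 1.020 the other way). On the risk-difference scale, one patient is 1/65 = 0.015, or 13% of 0.115.

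**5. Lower response rate.** Protocol Appendix 10.3 gives a pooled historical rate of 54.1%, and 0.541 × 65 ≈ 35 responders. With 35/35 the lower 90% limit is 0.766; with 34/35 the RR is 0.971 and the limit is 0.741.

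**6. Exclusion is not the same as imputation.** Removing three BI 695501 responders gives (49/62)/(52/65) = 0.988. Counting them as non-responders gives (49/65)/(52/65) = 0.942.

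**The case against.** The best reply is that NRI is a term the protocol defines, that SAP 15.1.2 adopts the NRI principle without saying its bullets are exhaustive, and that SAP 3.3 declares no change. On that reading the protocol rule comes in by reference and the SAP is merely an incomplete transcription. That may well be how the gap arose, but it does not close it. SAP 15.1.2 spells out when the imputation applies, and SAP 15.2.2 names the therapy trigger separately for Week 24, so the SAP did not treat it as implied.

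The reply is right that the case is narrow. It needs a major deviation with material effect on efficacy, within about four weeks, in a patient who stays on treatment and still shows a fall of 70 or more. The number may be zero.

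A reader might also infer more than the documents support:

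- That the restrictions are only advisory, because protocol 4.2.2.1 says investigators are encouraged to follow them. That sentence follows one on medication needed for a patient's safety; the table itself is worded as mandatory.
- That Step 2 of SAP 15.2.2 ("NRI principle will be considered at Week 24 as detailed in section 15.1.2") creates a second error at Week 24. Table 1 already fixes where each imputation applies.
- That these patients must stay non-responders at Week 24. The protocol's carry-forward sentence speaks of patients assessed as non-responders, which does not settle whether imputed ones are included, and protocol 7.5.1 leaves missing-data rules for secondary endpoints to the statistical plan.

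**Conclusion.** The omission is real and undeclared. For one type of patient the protocol and the SAP give opposite primary outcomes, and nothing in the SAP resolves it for Week 4. It should be fixed.

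It does not follow that the two documents will produce different results: the counts differ only if a qualifying patient exists. Nor is there support for saying the gap favours BI 695501. For this rule the SAP's responder count in each arm can only equal or exceed the protocol's, but the RR may move either way, and an equal number of patients in arms with equal response rates leaves it unchanged.

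The shift of about 0.02 per patient rests on assumed 80% response and an assumed number and arm. At that rate the lower limit stays above 0.76 with up to three BI 695501 patients affected; at about 54% a single patient could carry it from 0.766 to 0.741. Neither is a prediction. Protocol 7.2 sets no confirmatory hypothesis and protocol 7.3.1 uses 0.76 descriptively, so what is affected is the reported estimate and that descriptive comparison.

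**What to change.** Add a third bullet to SAP 15.1.2 carrying over the protocol 7.5.1 therapy-deviation criterion, with its reference to protocol Table 4.2.2.1: 1 and its timing before the Week 4 assessment. The protocol does not define which deviations are major or which therapies matter enough. State therefore that qualifying deviations are flagged by blinded medical review before the Week 4 snapshot. This timing needs its own sentence: SAP 5.4 sets it only for per-protocol violations, and SAP 9.1 sets none.

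If leaving the criterion out is intended, declare and justify that in SAP 3.3 instead.

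Optionally, say in SAP 15.2.2 whether patients classified this way at Week 4 remain non-responders at Week 24.

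The cost is one bullet and one sentence on timing, or one declared change. Concomitant medication and prohibited treatments are already recorded, so no new data are needed. The downside is some extra blinded medical judgement and possibly slightly lower response rates.

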15.1.3. PRIMARY ANALYSIS OF PRIMARY EFFICACY VARIABLE

The primary efficacy analysis will be performed for the FAS. Patients will be assigned to the treatment they were randomized to receive.

The primary objective of this trial is to compare the clinical efficacy of BI 695501 with EU-approved Humira in patients with active CD at the end of the induction phase at Week 4 by means of the Relative Risk (RR).

The primary analysis of the observed proportion of patients with a clinical response (CDAI decrease of ≥ 70 compared with baseline) at Week 4 will be based on log-linked binomial model.

The statistical model can be described as follows:

- (M1) Response to treatment at Week 4 = treatment + prior infliximab exposure + screening SES-CD

This model includes the stratification factor, prior exposure to infliximab, and treatment as fixed effects and screening SES-CD will be included as a categorical effect:

- Treatment (BI 695501, EU-approved Humira)
- Prior exposure to infliximab (Yes/No)
- Screening SES-CD (< 16 or ≥ 16)

The relative risk estimate together with its 90% and 95% CI (ratio scale) will be produced. The following SAS code will be used:

```
proc genmod data=data_CDAI70 descend;  
  class CDAI70 (ref="N") TRTP (ref="HUMIRA") EXP_PRIO (ref="N") BAS_SES  
    (ref="<16") / param=GLM;  
  model CDAI70=TRTP EXP_PRIO SCR_SES / dist=binomial link=logit;  
  lsmeans TRT / ilink;
```

run;

Document: \\ieedc-
vnasc01\BIOSdata\Boehringer_Ingelheim\BI_695501\NVA96252\Biostatistics\Documentation\S
AP\BI1297.4 SAP FINAL v4.0_22MAY2019.docx

Author: Version Number: Final V4.0
Version Date: 22MAY2019

Template No: CS_TP_BS016 Revision 5 Reference: CS_WI_BS005
Effective Date: 01Apr2018

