7.7 DETERMINATION OF SAMPLE SIZE

The sample size determination is not based on a power calculation, but assures a precise estimation of the relative risk difference. For this trial a precision (distance from observed difference to confidence limit) of 0.115 has been considered necessary and sufficient by the project team. Assuming a response rate of 80%, in both the Humira as well in the BI 695501 treatment arm, the trial will need at least 130 patients (65 per treatment arm).

Page 68 of 93

Proprietary confidential information © 2017 Boehringer Ingelheim International GmbH or one or more of its affiliated companies

Table 7.7: 1Precision of 90% CI

Assumed true response rate		Sample size	Precision ^{\$}	Relative risk (RR)	90% CI
Humira	BI 695501				
85%	85%	65	0.103	1	0.897-1.103
85%	80%	65	0.118	0.941	0.823-1.059
85%	75%	65	0.115	0.882	0.767-0.997
80%	80%	65	0.115	1	0.885-1.115
80%	75%	65	0.120	0.938	0.818-1.058
75%	75%	65	0.125	1	0.875-1.125

⁵Precision is defined as the distance from observed difference to confidence limit. Note that the precision is independent of the actual point estimate.

Calculations performed with nQuery Advisor® 7.0

Table 7.7: 2Precision of 95% CI

Assumed true response rate		Sample size	Precision ⁸	Relative risk (RR)	95% CI
Humira	BI 695501				
85%	85%	65	0.123	1	0.877-1.123
85%	80%	65	0.140	0.941	0.801-1.081
85%	75%	65	0.136	0.882	0.746-1.081
80%	80%	65	0.138	1	0.862-1.138
80%	75%	65	0.143	0.938	0.795-1.081
75%	75%	65	0.149	1	0.851-1.149

^{\$}Precision is defined as the distance from observed difference to confidence limit. Note that the precision is independent of the actual point estimate.

Calculations performed with nQuery Advisor[®] 7.0

Page 69 of 93

Proprietary confidential information © 2017 Boehringer Ingelheim International GmbH or one or more of its affiliated companies

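### The primary risk ratio is specified from a log-linked binomial model but coded with a logit link; with the stated link, the fit has a material chance of landing on its boundary at the planned 80% response, and no replacement estimator is named

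*SAP*

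**What the plan says.** Protocol 7.1 and 7.3.1 and SAP 15.1.3 name one estimator for the primary endpoint. The analysis "will be based on log-linked binomial model", with the model "Response to treatment at Week 4 = treatment + prior infliximab exposure + screening SES-CD". The protocol left open whether SES-CD enters as a continuous or categorical term; the SAP settles this: "screening SES-CD will be included as a categorical effect". The required output is the same in both documents: "The relative risk estimate together with its 90% and 95% CI (ratio scale) will be produced".

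The SAS code that SAP 15.1.3 says will be used fits a different link, "dist=binomial link=logit", followed by `lsmeans TRT / ilink`. Its variable names also disagree: `BAS_SES` in the class statement but `SCR_SES` in the model, and `TRTP` in the model but `TRT` in the lsmeans statement.

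Protocol 7.7 plans 65 patients per arm: "Assuming a response rate of 80%, in both the Humira as well in the BI 695501 treatment arm". Tables 7.7: 1 and 7.7: 2 add rows from 75% to 85%.

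Neither document says what happens if the model does not converge. The per-protocol sensitivity analysis in protocol 7.3.1 changes the population, not the estimator, and SAP 3.3 plans no change from the protocol.

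**The concern.** Two defects sit in one section, and the second becomes live once the first is repaired.

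First, the code does not do what the text says. With a logit link the treatment coefficient is a log odds ratio, and the `ilink` option back-transforms each arm's mean to a probability. Neither is the specified RR, and no RR interval follows from the code as printed.

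Second, a log-linked binomial model requires every fitted probability to stay at or below 1. When response is high and some covariate cells are small, the likelihood may have its maximum exactly at that limit. Standard software may then not converge, and model-based standard errors are not valid.

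At stake is who chooses the substitute, and when. The primary fit is first run on the unblinded Week 4 snapshot (protocol 7.4.1, SAP 4.1). Without a written rule, any replacement is chosen with treatment results in view.

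**Working it through.** **1. The plan's own figure.** Protocol 7.7 states "a precision (distance from observed difference to confidence limit) of 0.115" for 65 per arm at 80% in both arms. The 90% half-width is

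1.645 × √(0.80×0.20/65 + 0.80×0.20/65) = 1.645 × 0.0702 = 0.1154.

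This matches the stated 0.115, on the risk-difference scale. The inputs 65 per arm and 80% are therefore the right ones to carry forward.

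**2. Why the boundary is within reach.** The model has 4 parameters (intercept, treatment, prior infliximab, SES-CD category) over 2×2×2 = 8 cells. The documents give no stratum shares, so these are assumed. With 10% prior infliximab and 30% with SES-CD ≥16, the smallest cell expects 65 × 0.10 × 0.30 = 1.95 patients per arm. At 80% response, two patients both respond with probability 0.80² = 0.64. A cell made up only of responders is necessary for a boundary fit but not sufficient, because the cells share parameters. At 80%/80% at least one such cell occurred in 28-94% of simulated data sets.

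**3. Simulation.** For each scenario 1,500 trials of 65 per arm were generated and the log-binomial likelihood was maximised subject to fitted probabilities ≤1. A fit was counted as on the boundary when the largest linear predictor exceeded -0.001, which is a fitted probability of essentially 1. Assumptions, none of them in the documents:
- prior infliximab 10, 25 or 40%
- SES-CD ≥16 in 30 or 50%
- response ratios for the two factors (prior infliximab / SES-CD) of 1/1, 0.90/0.95 or 0.85/0.90.

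| Response rates (Humira / BI 695501) | Where it comes from | Fits on the boundary |
|---|---|---|
| 80% / 80% | planning assumption, protocol 7.7 | 4-24% |
| 85% / 80% | sensitivity row, Table 7.7: 1 | 9-46% |
| 85% / 85% | sensitivity row, Table 7.7: 1 | 13-59% |
| 75% / 75% | sensitivity row, Table 7.7: 1 | 2-18% |
| 54.1% / 54.1% | pooled historical rate, protocol 10.3 | 0-4% |

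With no stratum effects at all, the range is 9-24% at 80%/80% and 22-37% at 85%/85%, so the problem does not need strong prognostic strata.

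**4. Cross-check.** A different optimiser with stratified 1:1 allocation gave 6-24% at 80%/80% and 20-52% at 85%/85%. Unconstrained iteratively reweighted least squares, closer to what default software does, produced no valid fit in 4-21% and 12-39% respectively. SAS GENMOD itself was not available.

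**The case against.** **The code uses a logit link, so it has no such boundary.** This stands as a description of the code. It does not rescue the plan: the code contradicts the text of the SAP and the protocol, is not offered as a fallback, and does not yield the RR or its intervals. Either way, SAP 15.1.3 has to be edited.

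**The size rests on assumptions.** This also stands. Stratum shares and effects are not in the documents, and some 80%/80% settings give only about 4%. A reader might infer a far larger risk by choosing stronger effects. With 30% prior infliximab, 40% SES-CD ≥16 and ratios of 0.75 and 0.85, boundary rates at 85% response reach about 80%. But that puts the true response in the best cell at 0.85/(0.925 × 0.94) = 0.978, almost on the boundary already. The documents do not support such a scenario, and 85% is a sensitivity row, not the planning rate.

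**Observed response may be lower.** The only response data in the documents pool to 54.1%, where the risk is 0-4%, and non-responder imputation can only lower the observed rate. That is fair. Still, the plan ought to work at the rate on which it was sized.

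**The primary RR would not vanish.** A reader might infer that the RR cannot be estimated at all. That is too strong. A constrained maximum-likelihood RR exists on the boundary; in boundary fits at 80-85% response its logarithm differed from a stratified Mantel-Haenszel log-RR by a median of 0.02-0.05. What fails is ordinary convergence and the Wald interval.

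**Little hangs on it.** Protocol 7.2 sets no confirmatory hypotheses, the comparison with 0.76 in protocol 7.3.1 is descriptive, and the synopsis also plans a risk difference with intervals for the primary endpoint. This limits the consequence. It does not supply a substitute for the RR.

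**Conclusion.** The point holds in two parts. The contradiction between the log link in the text and the logit link in the code is certain, and the code as printed does not deliver the specified RR with its 90% and 95% intervals. If the stated log link is implemented, the fit lies on the boundary in roughly 4-24% of trials at 65 per arm and 80% response. That figure rests on assumed stratum shares and effects and on the 80% rate being realised; the risk is higher at 85% and close to nil at 54.1%.

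The consequence is an estimator for a descriptive primary RR chosen after unblinding. A reader might infer loss of a confirmatory test, but the documents define none. This is a cheap improvement, worth making before the Week 4 snapshot is unblinded.

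**What to change.** In SAP 15.1.3:
- Make the text and the code agree on the link, and correct the mismatched variable names.
- Specify an RR estimator with the same covariates that does not have this boundary failure. Either modified Poisson regression (log link, robust variance), or logistic regression with marginal standardisation to an RR and delta-method or bootstrap intervals, would do. Give 90% and 95% intervals in both cases.
- Use it as the primary method. If the log-binomial model is kept, name it as the replacement, with the trigger written down: no convergence, or any fitted probability reaching 1.

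The cost is a few sentences and a few lines of code. No new data are needed. Modified Poisson may lose a little efficiency. If the logistic route is taken, the existing model statement can largely stay, but the standardisation step and the RR intervals must be added. Protocol 7.1 and 7.3.1 name the log-linked model, so if the primary method changes, SAP 3.3 should record it as a change from the protocol.

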3.3.1 Main diagnosis for trial entry

Patients must have moderately to severely active CD (CDAI 220-450), confirmed by endoscopy or radiologic evaluation for more than 4 months, with evidence of mucosal ulceration documented by recorded ileocolonoscopy during trial screening.

Please refer to Section 8.3.1 (Source documents) for the documentation requirements pertaining to the in- and exclusion criteria.

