7.6 RANDOMIZATION

Patients who meet all the inclusion criteria and none of the exclusion criteria will be randomized 1:1 to either BI 695501 or EU-approved Humira over the 24-week (4-week induction and 20-week maintenance) treatment period after the screening period at Visit 2. The randomization will be stratified by prior exposure to infliximab (Yes/No) and screening SES-CD (<16 or \geq 16).

Randomization will occur on Day 1 (-1/+2) through a standard randomization visit call. Patients will be randomized to each treatment in a 1:1 ratio (BI 695501: EU-approved Humira) using an IRT system.

Boehringer Ingelheim Pharma GmbH & Co. KG, Clinical Trial Supply Unit or a third party appointed by the sponsor will provide the randomization list using a validated randomization number generating system. Access to the randomization code will be controlled and documented. All persons directly involved in the conduct of the trial have no access to the treatment allocation prior to final database lock. The block sizes of the randomization will be documented in the CTR.

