7. STATISTICAL CONSIDERATIONS

7.1. ADJUSTMENTS FOR COVARIATES AND FACTORS TO BE INCLUDED IN ANALYSES

The following covariates and factors are used in the primary and secondary efficacy analyses. For details of their inclusion in the models, see the specific analysis section.

- Treatment (BI 695501 versus EU-approved Humira)
- Prior exposure to infliximab (Yes/No).
- Baseline SES-CD (<16 or ≥16)

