10. DEMOGRAPHIC AND OTHER BASELINE CHARACTERISTICS

No statistical testing will be carried out for demographic or other baseline characteristics.

The following demographic characteristics will be reported at Primary Analysis for the FAS, PPS and SAF, and at Final Analysis for RND, FAS, PPS, PPS2 and SAF:

- Age (years) at Informed Consent
- Gender (Male/Female)

Document: \\ieedc-vnasc01\BIOSdata\Boehringer_Ingelheim\BI_695501\NVA96252\Biostatistics\Documentation\SAP\BI1297.4 SAP FINAL v4.0_22MAY2019.docx

Author: Version Number: Final V4.0
Version Date: 22MAY2019

Template No: CS_TP_BS016 Revision 5
Effective Date: 01Apr2018

Reference: CS_WI_BS005

Statistical Analysis Plan

- Childbearing potential (Post-Menopausal/Surgically Sterile/Childbearing Potential (tubal ligation at least 6 weeks before screening is considered not of childbearing potential))
- Race (American Indian or Alaska Native/Asian/Black or African American/Native Hawaiian or Other Pacific Islander/White/Other)
- Ethnicity (Hispanic or Latino/Not Hispanic or Latino/Not reported/Unknown)
- Country
- Weight at baseline (kg)
- Height at baseline (cm)
- BMI at baseline (kg/m²)

The randomization stratification categories (Prior exposure to infliximab Yes/No, screening SES-CD <16/≥16) based on eCRF data, will be presented at Primary and Final Analyses for the FAS. Any differences between stratification data in the eCRF and IVRS will be documented.

The following baseline disease characteristics will be presented at Primary Analysis for the FAS, PPS, SAF, and at Final Analysis for FAS, PPS2, and SAF:

- CDAI score at baseline as collected in the eCRF
- Mucosal ulceration at baseline as collected in the SES-CD under the item: Extent of ulcerated surface subscore. The second reading will be taken into account in case there were two readings.

Other baseline characteristics will be presented on FAS and SAF:

- Infection screen (for HBsAg, HCV and HIV test)
- Chest X-Ray result
- Tuberculosis (TB) test
- CRP at baseline
- Fecal calprotectin at baseline

Document: \\ieedc-
vnasc01\BIOSdata\Boehringer_Ingelheim\BI_695501\NVA96252\Biostatistics\Documentation\S
AP\BI1297.4 SAP FINAL v4.0_22MAY2019.docx

Author: Version Number: Final V4.0
Version Date: 22MAY2019

Template No: CS_TP_BS016 Revision 5
Effective Date: 01Apr2018

Reference: CS_WI_BS005

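### Baseline CDAI, the starting value of the primary endpoint, is not in the primary model; adjusting for it would be a cheap improvement of small and uncertain size

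*SAP*

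**What the plan says.** SAP 15.1.3 specifies M1 as "Response to treatment at Week 4 = treatment + prior infliximab exposure + screening SES-CD", with SES-CD split at 16. Protocol 7.3.1 has the same three terms. SAP 7.1 introduces its list with "The following covariates and factors are used in the primary and secondary efficacy analyses" and names only treatment, prior infliximab and SES-CD. The design controls the same two factors. Protocol 7.6 states: "The randomization will be stratified by prior exposure to infliximab (Yes/No) and screening SES-CD".

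The endpoint is built on baseline CDAI. SAP 15.1.1 defines "Decrease = CDAI at Baseline - CDAI at Week 4" and calls a patient a responder when this is 70 or more. SAP 5.3 admits to the FAS only patients with the CDAI measures at baseline and at Week 4. SAP 10 already tabulates "CDAI score at baseline as collected in the eCRF".

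The visible text gives no reason for leaving baseline CDAI out of M1 and describes no CDAI-adjusted analysis. Parts of the SAP are redacted, so such an analysis may exist there, but it would not alter M1.

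**The concern.** When an outcome is a change from a baseline value, that value is usually considered as a covariate. The slope of the decrease on baseline CDAI equals 1 minus the slope of Week 4 CDAI on baseline. Baseline is therefore unrelated to the decrease only if baseline differences persist in full to Week 4. Otherwise, patients who start higher tend to fall further and are more likely to be counted as responders.

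Two things are at stake. The first is precision, which is the only sample-size criterion in Protocol 7.7: there is no power calculation, only a target half-width of 0.115. The second is chance imbalance. With 65 per arm, the arms can differ somewhat in mean baseline CDAI, and M1 does nothing to remove the effect of that on the estimate.

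**Working it through.** **Inputs from the documents.** 65 per arm, 80% response in both arms and a 90% CI half-width of 0.115 (Protocol 7.7). CDAI of 220 to 450 at entry (Protocol 3.3.1). Pooled historical response of 54.1% (Protocol 10.3), rounded to 54% as a second scenario.

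**Inputs that must be assumed.** The documents do not give the prognostic strength of baseline CDAI, so two simulations cover a range in two ways. Both compare M1 with M1 plus continuous baseline CDAI.

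**Step 1: the plan's own figure.** Half-width = 1.645 × √(2 × 0.8 × 0.2 / 65) = 1.645 × 0.0702 = 0.1154. This reproduces the stated 0.115 as a risk-difference half-width.

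**Step 2: precision by slope.** 1,500 trials per scenario; baseline CDAI normal with mean 310 and SD 55, limited to 220–450; residual SD 85. Equivalent sample size = 1/(1 − gain)².

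| Slope of decrease on baseline | Gain in SE at 80% response | Equivalent sample size | Gain in SE at 54% response |
|---|---|---|---|
| 0.2 | −0.4% | 1/1.004² = 0.99 | 0.5% |
| 0.4 | 0.9% | 1/0.991² = 1.02 | 1.4% |
| 0.6 | 2.6% | 1/0.974² = 1.05 | 3.1% |
| 0.8 | 4.1% | 1/0.959² = 1.09 | 7.0% |

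**Step 3: precision by odds ratio per SD of baseline CDAI.** Standardised logistic estimates, 3,000 trials, 80% response. Each stratum factor has 30% prevalence, no effect on response and no correlation with CDAI.

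| Odds ratio per SD | 90% half-width, M1 | With CDAI | Variance ratio |
|---|---|---|---|
| 1.0 | 0.1165 | 0.1171 | 1.01 |
| 1.25 | 0.1168 | 0.1168 | 1.00 |
| 1.5 | 0.1164 | 0.1154 | 0.98 |
| 2.0 | 0.1147 | 0.1118 | 0.95 |
| 2.5 | 0.1145 | 0.1109 | 0.94 |

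The half-widths are for the risk difference. Variance ratios for log RR agree to within 0.002. At the last row, the saving is 130 × (1 − 0.938) ≈ 8 patients. At the first row, one useless covariate costs about 1/(130 − 5) = 0.8% in variance, in line with the simulated 1%. A modified-Poisson check (1,000 trials) gave variance ratios of 1.02, 1.00 and 0.92 for odds ratios of 1.0, 1.5 and 2.0.

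**Step 4: chance imbalance.** The SD of the between-arm difference in mean baseline is √(2/65) = 0.175 of a patient-level SD, so two SDs is 0.35. The resulting shift in the risk difference at 80% response is:

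| Odds ratio per SD | Shift under M1 | Shift with CDAI (absolute) |
|---|---|---|
| 1.25 | 0.011 | 0.001 |
| 1.5 | 0.023 | 0.000 |
| 2.0 | 0.033 | 0.004 |

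As a hand check at 1.5, p(1 − p) × ln(1.5) × 0.35 = 0.16 × 0.405 × 0.35 = 0.023. At an odds ratio of 1.0, where the true shift is zero, both models show 0.004, so values of that size are simulation noise. At 2.5 the shift goes from 0.038 to 0.008. Relative to 0.115, the M1 shifts in the table run from 0.011/0.115 = 10% to 0.033/0.115 = 29%.

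**Step 5: can CDAI go into the log-link model?** At 80% response, a simple log-binomial fitter (not SAS) failed in 6–9% of trials for M1. With CDAI added it failed in 38%, 76% and 94% at odds ratios of 1.0, 1.5 and 2.0. In the Step 2 simulation, fits with CDAI failed in 28% of trials at 54% response and up to 92% at 80%.

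**The case against.** The strongest reply is that this is a preference. M1 contains treatment and both stratification factors, protocol and SAP agree on them, and randomisation makes M1 valid without baseline CDAI. Protocol 7.2 sets no confirmatory hypotheses. At odds ratios of 1.5 to 2.0, the half-width changes by only 0.001 to 0.003, which is unlikely to alter a descriptive reading. SAP 10 tabulates baseline CDAI, so a marked imbalance would be seen. All of this stands, and it is why the point is minor.

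The size of the gain also rests on assumptions. The simulations limit baseline CDAI to 220–450 or use a standard normal scale. Under Protocol 6.2.1 that range is checked at Visit 1.1, whereas SAP 6.2 takes the last value up to first dose and CDAI is evaluated again on Day 1. The analysed baseline can therefore fall outside the range. Any correlation of CDAI with SES-CD would also reduce the gain from the Step 3 figures.

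A reader might infer three stronger things that the documents do not support.
- **That M1 is biased or wrong.** It is not; the imbalance in question is chance imbalance.
- **That adjustment always gains precision at no cost.** With a weakly prognostic CDAI there is no gain and possibly a small loss, and the estimator has to change. The 7.0% gain in Step 2 belongs to the most favourable slope at 54% response, not the planned 80%.
- **That a patient entering at 220 has too little room to respond.** CDAI starts at 0 (Protocol 5.2.1) and such a patient responds on reaching 150, so the floor does not prevent a response.

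**Conclusion.** The omission is a fact, and correcting it is worthwhile but optional. At the planned 80% response and 65 per arm, adjustment changes the SE of log RR by between about −0.4% (a loss) and +4% (a gain), equivalent to roughly 0 to 9% more patients. If baseline CDAI predicts response only weakly (odds ratio per SD of about 1.25 or less), precision does not improve and the benefit is protection against imbalance. For odds ratios of 1.25 to 2.0, that protection reduces the effect of a two-SD imbalance from about 0.01–0.03 on the risk-difference scale to at most 0.004. The direction of these results is secure. Their size depends on a prognostic strength that the documents do not give.

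**What to change.** In SAP 15.1.3, pre-specify a logistic model with treatment, prior infliximab, SES-CD category and continuous baseline CDAI, using the same baseline value as the endpoint. Report the marginally standardised risk ratio and risk difference with 90% and 95% CIs, and state how the intervals are computed. Do not add CDAI to the log-link model.

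If this becomes the primary analysis, SAP 3.3, which now reports no change, must record it as a change from the protocol's log-linked binomial model. Otherwise, or if Week 4 data are already unblinded, add it as a sensitivity analysis and leave M1 as it is.

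The cost is SAP text, some programming and, for a primary analysis, a documented change. The standardised risk ratio would replace the direct log-link coefficient, and about 1% in variance could be lost if CDAI has no prognostic value. The practical step is short: the code in SAP 15.1.3 already sets a logit link, although the text calls for a log link. That mismatch is a separate matter, but it needs correcting in the same paragraph.
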